#### Study Period 1:

[figure not shown]
- Days 1 to 10: oral balovaptan 10 mg qd
- Days 11 to 23 (or up to Day 30): no study drug

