### 9.2.2 Treatment Grouping

Period will refer to the analysis (treatment) period, as opposed to study period. This means that Study Period 2 will be divided in two analysis periods, Analysis Period 2 (Days -1 to 6) and Analysis Period 3 (Days 7 to 16). The study will therefore consist of 3 analysis periods. For Analysis Period 3, the analysis day will also be adjusted by subtracting 6 from the study day. Thus, Period 3 will have Analysis Days 1 to 10.

Label	Grouping
Analysis Period	
Study Drug	Balovaptan (reference), rifampicin, balovaptan + rifampicin (test)
Treatment	Treatment S: 10 mg balovaptan Treatment I: 600 mg rifampicin Treatment S+I: 10 mg balovaptan + 600 mg rifampicin

S= Substrate, I= Index Inducer

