#### 17.1.1 Adverse Events

All AEs will be coded to the current version of Medical Dictionary for Regulatory Activities (MedDRA, the latest version) by F. Hoffmann-La Roche, Ltd.

All AE summaries will include only treatment emergent adverse events (TEAEs). Treatment-emergent adverse events are those which occur after the first dose of study drug. AEs starting prior to medication dosing in the first period will be regarded as pre-dose AEs (i.e. non-TEAEs).

TEAEs occurring following dosing in a specific analysis period but before dosing in the next analysis period will be attributed to that specific analysis period, thus to the last received treatment. If the time is missing for an AE on a dosing day then the AE will be attributed to the treatment given on that day.

All adverse events (including non-TEAEs) recorded on the eCRF will be listed (including analysis period and treatment information). Pre-dose AEs will be presented in a separate listing. In addition, a separate listing of AEs leading to withdrawal from study will be provided.

TEAEs will be tabulated by system organ class and preferred term: one table with all TEAEs (number and percentage of subjects) overall and by treatment; one table with related TEAEs (number and percentage of subjects) by treatment; one table with all TEAEs (number and percentage of subjects) by treatment and relationship to study drug; one table with TEAEs (number and percentage of subjects) by treatment and severity.

Subjects are counted once, per preferred term per treatment, for the most severe of multiple occurrences (in case of severity) or most drug-related event (in case of relationship) of a specific MedDRA term. AEs

whose causal relationship was characterized as 'Yes'/'No' will be regarded as being related/not related to the study medication.

The following missing data will be imputed as defined (for calculations only / will not be presented):

- Missing AE start and / or end times for the calculation of onset and duration will be assumed to be at 00:01 for a start time and 23:59 for end times
- Missing AE severity or relationship will be assumed to be severe or related, respectively
- Missing AE start times for the determination of treatment emergence will be assumed to occur after treatment unless partial date documents the AE as happening prior to treatment

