- Missing AE start times for the determination of treatment assignment will be assumed to occur after treatment on the recorded date one minute after dosing
- Missing AE start date will be attributed to the treatment from analysis period 1 unless the AE end date occurs before first IMP administration

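### Adverse events with no start date are counted under balovaptan alone, even when first reported after rifampicin or the combination was given

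*SAP*

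**What the plan says.** SAP 17.1.1 closes its list of imputation rules with this one: "Missing AE start date will be attributed to the treatment from analysis period 1 unless the AE end date occurs before first IMP administration".

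The periods are fixed elsewhere in the SAP. In Study Period 1 the treatment is "Days 1 to 10: oral balovaptan 10 mg qd". Section 9.2.2 labels the study drugs "Balovaptan (reference), rifampicin, balovaptan + rifampicin (test") and adds: "Study Period 2 will be divided in two analysis periods, Analysis Period 2 (Days -1 to 6) and Analysis Period 3 (Days 7 to 16"). Analysis Period 1 is therefore balovaptan alone (the reference), Analysis Period 2 is rifampicin alone, and Analysis Period 3 is the combination (the test).

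For events with a known onset, 17.1.1 works differently. An event that starts after dosing in one analysis period and before dosing in the next "will be attributed to that specific analysis period, thus to the last received treatment". Treatment-emergent events are then tabulated by treatment in four tables.

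**The concern.** The missing-date rule takes no account of when the event surfaced. An undated event first mentioned during combination dosing, or at the follow-up visit, is placed under balovaptan alone. Had its true onset been known and fallen in that interval, the general rule would have placed it under the combination.

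Two neighbouring rules lean towards caution: "Missing AE severity or relationship will be assumed to be severe or related, respectively". The missing-date rule has no comparable rationale for the contrast between treatments. It can add events to the reference and remove them from the other two columns, but never the reverse.

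What is at stake is the secondary objective on safety and tolerability of balovaptan alone and with rifampicin. Protocol 1.3 expects that exposure to some metabolites may rise under rifampicin, so the combination column is the one a reader will look at. The protocol names headache both as balovaptan's most frequent adverse event (1.3) and as a common event with rifampicin (3.3.2.2). A misplaced undated headache would therefore not stand out.

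**Working it through.** The documents give no figure for this rule, so there is none to reproduce. The check has three parts.

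**1. Apply the rule to every possible case.** The only input is the end date.

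| True onset | Possible end date | Column under the rule | Column by true onset |
|---|---|---|---|
| Before first dose | Before first dose | Pre-dose, not in the tables | Pre-dose |
| Before first dose | Any later period, or ongoing | Balovaptan alone | Pre-dose |
| Analysis Period 1 | Period 1, 2 or 3, or ongoing | Balovaptan alone | Balovaptan alone |
| Analysis Period 2 | Period 2 or 3, or ongoing | Balovaptan alone | Rifampicin |
| Analysis Period 3 | Period 3, or ongoing | Balovaptan alone | Combination |

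An event that began in Period 2 or 3 cannot have ended before the first dose, so the exception never rescues it. All such events are misplaced.

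**2. See whether another rule in 17.1.1 overrides it.**

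- The last-received-treatment rule needs an onset date.
- The missing-time rule for choosing the treatment needs one too: "Missing AE start times for the determination of treatment assignment will be assumed to occur after treatment on the recorded date one minute after dosing".
- Partial dates appear only in the rule that decides whether an event is treatment-emergent: "Missing AE start times for the determination of treatment emergence will be assumed to occur after treatment unless partial date documents the AE" as earlier than treatment. They are not used to choose the treatment, and the SAP does not say whether a partial date counts as missing.

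None of these overrides the missing-date rule.

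**3. Size.** Let w be the washout (14 to 21 days, SAP 6.0) and f the time from last dose to follow-up (14 to 21 days, SAP 6.0; reporting runs up to 21 days after the last dose, Protocol 5.3.1). The days that the general rule would attribute to each treatment are:

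- Balovaptan alone: 10 + w − 1 = 23 to 30
- Rifampicin alone: 6
- Combination: 10 + f = 24 to 31

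| w | f | Total days | Balovaptan alone | Rifampicin | Combination | Outside Period 1 |
|---|---|---|---|---|---|---|
| 14 | 14 | 23+6+24 = 53 | 43.4% | 11.3% | 45.3% | 56.6% |
| 14 | 21 | 23+6+31 = 60 | 38.3% | 10.0% | 51.7% | 61.7% |
| 21 | 14 | 30+6+24 = 60 | 50.0% | 10.0% | 40.0% | 50.0% |
| 21 | 21 | 30+6+31 = 67 | 44.8% | 9.0% | 46.3% | 55.2% |

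If onset of undated events were uniform over these days, which is an assumption, 50% to 62% would be misplaced.

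Per subject, with 16 exposed in a column, 1/16 = 6.25 percentage points. If the moved subject leaves the combination count and enters the reference count, the gap between the two columns changes by 2 × 6.25 = 12.5 points. That is a maximum. Subjects are counted once per preferred term per treatment, so a column does not change if the subject already has that term there.

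**The case against.** The strongest reply is that the rule will rarely operate. Protocol 5.1.2.1 requires the onset date of each event to be documented. Adverse events are sought at every contact (5.3.1), all dosing is in-house, discrepant data are queried (7.1) and source data are verified (7.3). This stands, and it is the main reason the point is minor.

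The rule can also be called conservative in one respect: it makes an undated event treatment-emergent and charges it to the investigational drug given alone. That is fair as far as it goes, and the documents state no preferred direction of caution between the reference and the combination. But the combination also contains balovaptan, and there the rule undercounts.

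The listings offer some protection. All events are listed with analysis period and treatment, and imputed values are not shown, so a careful reader could find a blank start date beside an assigned treatment. No flag is planned, however, and the tables carry no sign of it.

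A reader might infer that undated events gather in the outpatient intervals, so that about half of them belong to the combination. The documents do not support this. Nothing in them says where undated events arise, and the half depends on the uniform-onset assumption. A reader might also apply 1/12 = 8.3 points. Twelve is the evaluable number for PK precision; SAP 9.1.3 bases percentages on subjects exposed within a treatment, so 12 would apply only if exposure in a column fell that far.

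**Conclusion.** The point holds as a minor defect. For treatment-emergent events the rule always yields balovaptan alone, whatever the date of first report. It departs from the SAP's own last-received-treatment principle and shifts undated events in one direction only. Rifampicin-alone events are moved as well as combination events.

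The number of events affected is unknown and should be small. Each one is worth up to 6.25 points in a 16-subject column, subject to the once-per-term count. The 50% to 62% range is illustrative and rests on uniform onset.

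It would be too strong to conclude that the safety comparison is materially biased. The secondary objective is to evaluate safety under each condition, SAP 9.4.3 plans no hypothesis test, and the adverse event tables are descriptive. The overall treatment-emergent column and the primary PK analysis are not affected by which treatment column an event is placed in.

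**What to change.** Replace the sentence in SAP 17.1.1, before database lock, with:

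*An AE with a missing start date is attributed to the last treatment received before the AE was first reported, within the limits set by any partial start date and the end date; AEs ending before first IMP administration are pre-dose. If the treatment still cannot be determined, the AE is assigned by one pre-stated default and flagged as imputed in the listing.*

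The rule should refer to the last treatment received, not to the analysis period in which the event was first recorded. Analysis Period 2 begins on Day -1, before any rifampicin is taken, so an event reported at re-admission would otherwise be charged to rifampicin. SAP 9.2.3 ends the last analysis period when follow-up starts, so an event first reported at Follow-up would otherwise belong to no period.

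Any default will favour one column, which is why it should be stated in advance and flagged. The new rule can still misplace an event that began early and was reported late; the partial start date and end date limit this.

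The cost is one SAP sentence, a little programming, and use of a first-report or visit date. The eCRF is not among the documents, so the availability of that date is an assumption to confirm.

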### 17.1.2 Deaths and Serious Adverse Events

A listing of deaths and other serious adverse events (SAE) will be provided by subject.

### 17.1.3 Laboratory Data

Clinical laboratory data will be presented using units from the study data tabulation model (SDTM) Controlled Terminology.

All laboratory data will be listed, including laboratory variables not listed in the protocol. A separate listing, including out-of-range values will also be provided. Normal ranges will be used directly from the clinical laboratory.

Descriptive statistics summarizing continuous laboratory results of clinical chemistry, hematology and urinalysis (observed and derived changes from baseline) by treatment and scheduled time will be provided. For categorical urinalysis parameters frequency tables, showing the number of subjects in a category (n) and the percentage of the total number of subjects per treatment (N), will be provided. Sporadic urinalysis tests that were performed when abnormalities were observed (i.e. microscopy/sediment) will only be listed.

### 17.1.4 Vital Signs

All vital signs data including derived changes from baseline will be listed.

Descriptive statistics will be provided to summarize vital signs including changes from baseline by treatment and scheduled time.

### 17.1.5 Electrocardiograms

All ECG parameters (including changes from baseline) and the corresponding abnormalities and physician's conclusions will be listed by subject.

The observed measurements for all ECG parameters (including T-wave, U-wave) and the corresponding abnormalities will be listed for all time points. The means of triplicate measurements for continuous parameters and the change from baseline of the mean triplicate measurements at each scheduled time point will be listed by subject.

Descriptive statistics will be provided to summarize mean continuous ECG parameters (observed and changes from baseline) by treatment and scheduled time. A frequency table will be provided as well to summarize the ECG parameters by physicians conclusion (normal, abnormal not clinically significant, abnormal clinically significant).

### 17.1.6 Columbia Suicide Severity Rating Scale

C-SSRS is a clinical tool used to assess the lifetime suicidality of a subject (C-SSRS lifetime version) as well as any new instances of suicidality (C-SSRS since last visit). It captures the occurrence, severity and

frequency of suicide-related thoughts and behaviors during the assessment period. All individual C-SSRS results will be listed.

## Appendix 1: Glossary of Abbreviations

Glossary of Abbreviations:	
AE	Adverse event
ADAE	Adverse Event Analysis Dataset
ADaM	Analysis data model
ADPC	PK Concentrations Analysis Dataset
ADPP	PK Parameters Analysis Dataset
ADSL	Subject Level Analysis Dataset
BMI	Body mass index
BQL	Below the quantifiable limit
CDISC	Clinical Data Interchange Standard Consortium
CI	Confidence interval
CRU	Clinical research unit
C-SSRS	Columbia Suicide Severity Rating Scale
CSR	Clinical study report
CV	Coefficient of variation
DBP	Diastolic Blood Pressure
ECG	Electrocardiogram
eCRF	Electronic case report form
EDS	Early Development Services
FSH	Follicle-stimulating hormone
HIV	Human immunodeficiency virus
HBsAg	Hepatitis B virus surface antigen

HCV	Hepatitis C virus
ICH	The International Conference on Harmonization of Technical Requirements for Registration of Pharmaceuticals for Human Use
LLOQ	Lower limit of quantification
MedDRA	Medical Dictionary for Regulatory Activities
M2, M3	Metabolites
PK	Pharmacokinetic
QA'd	Quality assured
QC'd	Quality controlled
qd	Once daily
SAP	Statistical analysis plan
SAE	Serious adverse event
SBP	Systolic Blood Pressure
SD	Standard deviation
SDTM	Study data tabulation model
TEAE	Treatment-emergent adverse event
TFL(s)	Tables, figures and listings
WNL	WinNonlin

### Appendix 2: Schedule of Assessments

Assessments	Washout of minimally 14 and maximally 21 days between the study periods													
	Screening	Period 1					Period 2							Follow-up
	Day -21 to Day -2	Day -1	Days 1-9	Day 10	Day 11	Washout: for 14-21 days after last dose	Day -1	Days 1-5	Day 6	Day 7	Days 8-15	Day 16	Day 17	Days 30 – 37 of Period 2
Written informed consent	X													
Inclusion and exclusion criteria	X													
Demographics	X													
Medical history	X													
Medication history	X													
Study drug administration: balovaptan a			X	X					X	X	X			
Study drug administration: rifampicin a								X	X	X	X	X		
Standardized meals b				X					X			X		
Pharmacokinetic sampling balovaptan c			X	X	X						X	X	X	
Clinical genotyping sample		X												
Pharmacokinetic sampling rifampicin d									X	X		X	X	
Physical examination	X e				X		X f						X	X f
Triplicate 12-lead ECG g	X	X	X	X	X		X	X	X	X	X	X	X	X
Vital signs h	X i	X i	X	X i	X i		X i	X	X	X	X	X i	X i	X i
Hematology j	X	X			X		X	X	X	X	X		X	X
Serum chemistry j	X	X			X		X	X	X	X			X	X
Urinalysis j	X	X			X		X						X	X
Coagulation	X						X							
Urine drug screen	X	X					X							
Urine alcohol test	X	X					X							
Serology	X													
Pregnancy test k	X	X					X							X
Resident at study center l		X	X	X	X		X	X	X	X	X	X	X	
Adverse event monitoring	X	←—————→					←—————→							X
Review concomitant medications	X	←—————→					←—————→							X
C-SSRS	X				X								X	

Abbreviations: BMI = body mass index; C-SSRS= Columbia Suicide Severity Rating Scale; ECG = electrocardiogram; qd = once daily;

- 
- a Study drugs will be administered after an overnight fast of at least 8 hours, 30 minutes prior to breakfast. On days rifampicin and balovaptan are coadministered, they will be administered at the same time. Water will be allowed ad libitum up to 1 hour prior to dosing and from 1 hour post dosing, and no food is allowed for at least 4 hours post dose—lunch, dinner, and afternoon/ evening snacks will be provided 4 or more hours after dosing.
  - b A standardized breakfast will be provided at least 30 minutes after dosing of balovaptan alone, rifampicin alone, or balovaptan + rifampicin together in either period. A standardized lunch and standardized dinner will be provided 4 and 10 hours post dose, respectively, in both periods. Standardized afternoon and evening snacks will be provided as well.
  - c Samples to measure the concentration of balovaptan, M2, and M3 (one sample per time point to measure all 3 analytes) will be taken at predose, and 0.5, 1, 1.5, 2, 2.5, 3, 4, 6, 8, 12, 16, 24, hours post dose on Days 10/11 of Period 1 (16- and 24-hour samples are on the morning of Day 11) and 16/17 of Period 2 (16- and 24-hour samples are on the morning of Day 17). A predose sample to measure the concentration of balovaptan, M2, and M3 will also be taken on Days 2, 4, 8, and 9 in Period 1, and on Days 8, 10, 14, and 15 in Period 2 (see also [Appendix 2](#)).
  - d Samples to measure the concentration of rifampicin will be taken predose and at 1, 1.5, 2, 3, 4, 6, 12, and 24 hours post dose of rifampicin on Days 6/7 and 16/17 of Period 2 (24-hour samples are on the morning of Days 7 and 17) (see also [Appendix 2](#)).
  - e Includes measurement of height, weight and BMI.
  - f Includes measurement of weight.
  - g Triplicate ECGs will be collected as follows: in Period 1, on Day -1 and predose and 3 hours after dosing of balovaptan on Days 3, 7, and 10 and in the morning of Day 11; and in Period 2, on Day -1, and predose and 3 hours post dose on Days 3, 6, 9, 13, and 16; in the morning of Day 17, and at Follow-up (see also [Appendix 2](#)).
  - h Vital signs will be collected as follows: in Period 1, on Day -1 and predose and 3 hours after dosing of balovaptan on Days 3, 7, and 10 and in the morning of Day 11; and in Period 2, on Day -1, and predose and 3 hours post dose on Days 3, 6, 9, 13, and 16; in the morning of Day 17, and at Follow-up (see also [Appendix 2](#)).
  - i Includes measurement of body temperature.
  - j Hematology and chemistry at Screening and on Days -1 and 11 of Period 1 and on Days -1, 3, 6, 9, 13, 17 in Period 2, and follow up. Urinalysis at Screening and on Days -1 and 11 of Period 1 and on Days -1 and 17 in Period 2 and at Follow-up.
  - k For females only: FSH and serum pregnancy test at Screening, and serum pregnancy test only at all other time points.
  - l Subjects will be admitted to the clinical research unit on Day -1 of Period 1 and Period 2 and will be discharged on Day 11 and Day 17 of Period 1 and 2, respectively, after completion of study assessments.

### Appendix 3: Schedule of PK, ECG and VS Measurements

Procedure Study Day	Predose or Prior to Admission/Discharge	Hours post dose a											
		0.5	1	1.5	2	2.5	3	4	6	8	12	16	24
Blood sampling balovaptan, M2, and M3 (one sample for all 3 analytes)													
Period 1													
Days 2, 4, 8, and 9	X b												
Day 10	X b	X	X	X	X	X	X	X	X	X	X	X	X c
Period 2													
Days 8, 10, 14, and 15	X b												
Day 16	X b	X	X	X	X	X	X	X	X	X	X	X	X d
Blood sampling rifampicin													
Period 2													
Day 6	X b		X	X	X		X	X	X		X		X e
Day 16	X b		X	X	X		X	X	X		X		X d
12-lead electrocardiograms													
Period 1													
Day -1 and Day 11	X f												
Days 3, 7, and 10	X b						X						
Period 2													
Day -1 and Day 17	X f												
Days 3, 6, 9, 13, and 16	X b						X						
Vital signs													
Period 1													
Day -1 and Day 11	X f												
Days 3, 7, and 10	X b						X						
Period 2													
Day -1 and Day 17	X f												
Days 3, 6, 9, 13, and 16	X b						X						

aFor sampling to measure balovaptan, M2, and M3, and for ECG and vital signs measurements on days balovaptan or balovaptan together with rifampicin are administered, post dose is relative to time of balovaptan dosing; for sampling to measure rifampicin and for ECG and vital signs measurements on days balovaptan is not administered, post dose is relative to time of rifampicin dosing

b10 minutes predose (or time matched, when not dosed)

cDay 11

dDay 17

eDay 7

fPrior to admission or discharge

## Appendix 4: List of End of Text Outputs

List of End of Text Tables and Figures:		
Output	Title	Population Set
Section 14.1 – Disposition and Demographic Data		
Table 14.1.1	Summary of Subject Disposition	Safety
Table 14.1.2.1	Summary of Demographics	Safety
Table 14.1.2.2	Summary of Demographics (if applicable)	PK
Section 14.2 – Pharmacokinetic Data		
Table 14.2.1	Individual Values and Descriptive Statistics of Balovaptan Plasma Concentrations	PK
Table 14.2.2	Individual Values and Descriptive Statistics of Balovaptan Plasma Parameters	PK
Table 14.2.3	Individual Values and Descriptive Statistics of Balovaptan Metabolite (M2, M3) Plasma Concentrations	PK
Table 14.2.4	Individual Values and Descriptive Statistics of Balovaptan Metabolite (M2, M3) Plasma Parameters	PK
Table 14.2.5	Individual Values and Descriptive Statistics of Rifampicin Plasma Concentrations	PK
Table 14.2.6	Individual Values and Descriptive Statistics of Rifampicin Plasma Parameters	PK
Table 14.2.7	Statistical Analysis of the effect of Rifampicin on Balovaptan	PK
Figure 14.2.8.1	Geometric Mean Balovaptan Plasma Concentrations versus Time (Linear and Semi-Logarithmic Scale)	Safety
Figure 14.2.8.2	Geometric Mean Balovaptan Metabolite (M2, M3) Plasma Concentrations versus Time (Linear and Semi-Logarithmic Scale)	Safety
Figure 14.2.8.3	Geometric Mean Rifampicin Plasma Concentrations versus Time (Linear and Semi-Logarithmic Scale)	Safety
Figure 14.2.9.1	Total Profile of Individual Balovaptan Plasma Concentrations versus Time (Linear and Semi-Logarithmic Scale)	Safety
Figure 14.2.9.2	Total Profile of Individual Balovaptan Metabolite (M2, M3) Plasma Concentrations versus Time (Linear and Semi-Logarithmic Scale)	Safety

Figure 14.2.9.3	Total Profile of Individual Rifampicin Plasma Concentrations versus Time (Linear and Semi-Logarithmic Scale)	Safety
Figure 14.2.9.4	Combined Total profile of Individual Balovaptan Plasma Concentrations versus Time (Linear and Semi-Logarithmic Scale)	Safety
Figure 14.2.9.5	Combined Total profile of Individual Balovaptan Metabolite (M2, M3) Plasma Concentrations versus Time (Linear and Semi-Logarithmic Scale)	Safety
Figure 14.2.9.6	Combined Individual Rifampicin Plasma Concentrations versus Time (Linear and Semi-Logarithmic Scale)	Safety
Figure 14.2.9.7	Individual Balovaptan Plasma Concentrations versus Time – Analysis Day 10 (Linear and Semi-Logarithmic Scale)	Safety
Figure 14.2.9.8	Individual Balovaptan Metabolite (M2, M3) Plasma Concentrations versus Time – Analysis Day 10 (Linear and Semi-Logarithmic Scale)	Safety
Section 14.3 – Safety Data		
Section 14.3.1 Adverse Events		
Table 14.3.1.1	Summary of TEAEs for Each System Organ Class and Preferred Term (Number and Percentage of Subjects) by Treatment	Safety
Table 14.3.1.2	Summary of Related TEAEs for Each System Organ Class and Preferred Term (Number and Percentage of Subjects) by Treatment	Safety
Table 14.3.1.3	Summary of TEAEs for Each System Organ Class and Preferred Term (Number and Percentage of Subjects) by Treatment and Relationship to Study Drug	Safety
Table 14.3.1.4	Summary of TEAEs for Each System Organ Class and Preferred Term (Number and Percentage of Subjects) by Treatment and Severity	Safety
Section 14.3.2 Lists of Deaths, Other Serious and Significant Adverse Events		
Table 14.3.2.1	Listing of Deaths and Other Serious Adverse Events	Safety
Section 14.3.3 Clinical Laboratory		
Table 14.3.3.1	Listing of Abnormal Laboratory Values	Safety
Table 14.3.3.2	Descriptive Statistics of Clinical Laboratory Results - Hematology	Safety
Table 14.3.3.3	Descriptive Statistics of Clinical Laboratory Results – Serum Chemistry	Safety
Table 14.3.3.4	Descriptive Statistics of Clinical Laboratory Results - Urinalysis	Safety
Section 14.3.4 Other Safety		
Table 14.3.4.1	Descriptive Statistics of Vital Signs	Safety
Table 14.3.4.2	Summary of 12-Lead Electrocardiogram	Safety
Table 14.3.4.3	Frequency of 12-Lead Electrocardiogram Physicians Conclusion	Safety

Table 14.1.4.4	Summary of Treatment Compliance	Safety
----------------	---------------------------------	--------

List of End of Text Listings:	
Output	Title
Section 16.2.1 – Disposition	
Listing 16.2.1	Subject Disposition
Section 16.2.2 – Protocol Deviations	
	Not part of TFL – Reserved for protocol deviations in CSR
Section 16.2.3 – Excluded Subjects	
Listing 16.2.3.1	Analysis Sets
Section 16.2.4 – Demographics and Baseline Characteristics	
Listing 16.2.4.1	Subject Demographics (including genotype)
Listing 16.2.4.2	Medical History
Listing 16.2.4.3	Prior and Concomitant Medications
Listing 16.2.4.4	Drug and Alcohol Screen
Listing 16.2.4.5	Serology Test Results
Listing 16.2.4.6	Pregnancy and Serum FSH Test Results
Listing 16.2.4.7	Genotyping Results
Section 16.2.5 – Compliance and Drug Concentration Data	
Listing 16.2.5.1	Study Dates
Listing 16.2.5.2	Study Drug Administration
Listing 16.2.5.3	Deviations from Inclusion/Exclusion criteria
Listing 16.2.5.4	PK Blood Sampling Time Deviations and Comments
Listing 16.2.5.5	Food Intake
Section 16.2.7 – Adverse Events Data	
Listing 16.2.7.1	Adverse Events
Listing 16.2.7.2	Adverse Events Leading to Withdrawal
Section 16.2.8 – Laboratory Data	
Listing 16.2.8.1	Clinical Laboratory Results – Hematology
Listing 16.2.8.2	Clinical Laboratory Results – Chemistry
Listing 16.2.8.3	Clinical Laboratory Results – Urinalysis
Listing 16.2.8.4	Clinical Laboratory Results – Coagulation
Section 16.2.9 – Other Safety Data	
Listing 16.2.9.1	Vital Sign Results
Listing 16.2.9.2	12-Lead Electrocardiogram Results

Listing 16.2.9.3	Abnormalities and Changes in Findings at the Physical Examinations
Listing 16.2.9.4	Columbia-Suicide Severity Rating Scale

Other Appendix Outputs:	
Output	Title
Appendix 16.1.7	Randomization
Appendix 16.1.9.2	Statistical Appendices

